## **5.8 ANALYSES TO BE CONDUCTED**

### **Disposition of Study Subjects**

Subject disposition will be summarized using counts and percentages. The number and percentage of subjects completed and discontinued along with the specific reasons for discontinuation will be tabulated.

### **Demographic and Baseline Characteristics**

Summary statistics will be provided for patient demographics and pre-operative surgical characteristics.

### **Primary and Secondary Endpoint Analyses**

The primary endpoint of stapler performance issues will be summarized by counts and percentages and a 95% confidence interval will be calculated.

Summary statistics as appropriate for continuous or categorical variables will be provided for assessments of surgical stress as measured by SURG-TLX, and a surgeon satisfaction questionnaire.

### **Analysis of Safety**

All AEs collected will be summarized with counts and percentages by MedDRA system organ class and preferred term. Device-related AEs and procedure-related AEs will also be summarized by MedDRA system organ class and preferred term. These summaries will also be presented for all serious adverse events reported during the study. All AEs will also be summarized by maximum severity by MedDRA system organ class and preferred term. The number and percentage of subjects requiring blood product transfusions will be summarized. Concomitant procedures and concomitant medications will be listed for all subjects.

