| 
Analysis of Effectiveness and Safety:
 | 
Analysis of Effectiveness
 
The primary endpoint is the number of subjects in whom a stapler performance issue is observed, where a stapler performance issue is defined as a failure of the powered circular stapler (study device) to perform per its IFU. This includes but is not limited to difficulty placing or removing the stapler, stapler misfire/failure of the device to fully fire, staple line defects, incomplete or thin donuts, tissue damage, positive intraoperative leak test, detached components, unformed staples, or any other device failure.
 
No formal hypothesis is being tested in this study.
 
The primary endpoint of stapler performance issues will be summarized by counts and percentages and a 95% confidence interval will be calculated.
 
Summary statistics as appropriate for continuous or categorical variables will be provided for assessments of surgical stress as measured by SURG-TLX and a surgeon satisfaction questionnaire.
 
Analysis of Safety
 
For this study, an adverse event is defined as any undesirable clinical occurrence in a subject that may be attributable to the study procedure or device used to create the colorectal anastomosis. Only AEs attributable to the device used to create the anastomosis or to the study procedure are to be recorded in the eCRF and reported to the Sponsor.
 
All adverse events reported during the study will be coded to the Medical Dictionary for Regulatory Activities (MedDRA). Adverse events will be summarized with counts and percentages by MedDRA system organ class and preferred term. Device-related AEs and procedure-related AEs will also be summarized by MedDRA system organ class and preferred term. These summaries will also be presented for all serious adverse events reported during the study. AEs will also be summarized by maximum severity by MedDRA system organ class and preferred term.
 |
| 
Interim Analysis:
                     | 
No interim analysis is planned.
   |

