### **Analysis of Subgroups**

Subgroup analyses are planned to be performed for prior radiation therapy/chemotherapy (presence or absence), procedure approach (open vs. laparoscopic), and indication for surgery (diverticulitis, neoplasm, etc.). Summary statistics for the procedure-related parameters will be provided for each subgroup. Further subgroups may be defined pending the distributions of baseline demographic and clinical characteristics.

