## **7.2 REPORTING PROCEDURES FOR ADVERSE EVENTS**

### **7.3 RECORDING ADVERSE EVENTS**

The Investigator will record all device- or procedure-related AEs considered attributable (relationship of possibly, related, or unknown) to the powered circular stapler or to the procedure in the source documents and associated eCRF. The site must complete the AE CRF within two weeks of becoming aware of an event and SAE eCRF within 72 hours of becoming aware of the event. Supporting SAE documentation should be de-identified and emailed to the Clinical Study Lead.

Standard medical terminology should be used when recording AEs. In addition, the following information should be recorded:

- Onset Date
- Resolution date or date of death
- Severity of the event
- Action Taken
- Event Status (ongoing at study end or resolved)
- Relationship of AE to a surgical device used in the study
- Relationship of AE to the study procedure
- Indication of whether the event is serious

Data related to SAEs will be collected until event resolution, or until the event is considered stable, or until all attempts to determine the resolution of the event are exhausted. All AEs that are unresolved at study completion (or early termination) will be recorded as ongoing at study end.

The Investigator will be required to assess if the SAE is considered anticipated (Appendix II) and if the event involved a product complaint. The report of an SAE by a site does not constitute an admission that study personnel or the user facility (hospital/clinic) caused or contributed to the event. The study site is also responsible for submitting to the reviewing IRB/EC according to their IRB/EC procedures.

The Investigator will be required to assess if the SAE is considered anticipated (Appendix II) and if the event involved a product complaint. The report of an SAE by a site does not constitute an admission that study personnel or the user facility (hospital/clinic) caused or contributed to the event. The study site is also responsible for submitting to the reviewing IRB/EC according to their IRB/EC procedures.

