## Revision History

Revision Number	Revision Date	Reasons for Revision
1.0	28JAN2020	Original Document
2.0	05FEB2020	Addition of Adverse Event tables to support the submission to NMPA for registration in China. These include differentiation of intraoperative (day of surgery) versus postoperative (strictly after surgery) and are described in mock-up Tables 29 to 33. Additional text has also been added to Section 8.5 to describe these tables.

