### 8.5 Safety Analyses

Safety will be assessed through the incidence of AEs and SAEs, which will be coded using the Medical Dictionary for Regulatory Activities (MedDRA). The number and percentage of subjects reporting AEs and SAEs will be summarized at the MedDRA system organ class and preferred term level. Similar summaries will also be provided for AEs and SAEs related to the study device, as well as for AEs and SAEs related to the study procedure. Related events are those where the relationship is indicated as Unlikely, Possibly, Probably, or Causal. Summaries will also be provided for AEs, device-related AEs and SAEs where the start date of the event is equal to the day of surgery (intraoperative AEs). Similar summaries will be generated for AEs and device-related AEs where the start date of the event is strictly after the day of surgery (postoperative AEs). All reported adverse events will be listed. Listings will also be provided for concomitant procedures and concomitant medications.

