## Appendix: Table Shells and List of Listings to be Generated

Table shells are provided below for all summaries to be generated for this study. These shells are a guide to the general layout of data to be presented. Minor modifications can be made to suit existing programs or macros that are available. Additionally, a list of all listings to be created is provided corresponding to the eCRFs that are used during this study. All fields collected will be listed.

Table 1  
Subject Disposition  
All Subjects

	Overall
Signed Informed Consent	xx
Full Analysis Set	xx
Completed the Study	xx (xx.x%)
Discontinued from the Study	xx (xx.x%)
Reason for Discontinuation	
Withdrawal of consent	xx (xx.x%)
Adverse Event	xx (xx.x%)
Death	xx (xx.x%)
Lost to Follow-up	xx (xx.x%)
Site or Study Termination	xx (xx.x%)
Other	xx (xx.x%)

All percentages are calculated using the number of subjects in the Full Analysis Set as the denominator.

*Programming note: Only categories actually observed in the database need to be displayed for Reason for Discontinuation.*

Table 2  
 Subject Demographics and Vital Signs  
 Full Analysis Set

Characteristic	Overall (N = ##)
Age at Consent (yrs)	
N	xx
Mean (SD)	xx.x (xx.x)
Median (Min, Max)	xx.x (xx, xx)
Gender, n (%)	
Male	xx (xx.x%)
Female	xx (xx.x%)
Ethnicity, n (%)	
Hispanic or Latino	xx (xx.x%)
Not Hispanic or Latino	xx (xx.x%)
Not Reported	xx (xx.x%)
Race, n (%)	
Race 1	xx (xx.x%)
.....	xx (xx.x%)
Height (cm)	
n	xx
Mean (SD)	xx.x (xx.x)
Median (Min, Max)	xx.x (xx, xx)
Weight (kg)	
n	xx
Mean (SD)	xx.x (xx.x)
Median (Min, Max)	xx.x (xx, xx)
Body mass index (kg/m  )	
n	xx
Mean (SD)	xx.x (xx.x)
Median (Min, Max)	xx.x (xx, xx)

Denominator and percentages are based on subjects with non-missing data.

Table 3  
 Medical History By System Organ Class and Preferred Term  
 Full Analysis Set

System Organ Class	Preferred Term	Overall (N = ##)
Total		xx (xx.x%)
System Organ Class 1		xx (xx.x%)
	Preferred Term 1	xx (xx.x%)
	Preferred Term 2	xx (xx.x%)
	Preferred Term 3	xx (xx.x%)
System Organ Class 2		xx (xx.x%)
	Preferred Term 1	xx (xx.x%)
	Preferred Term 2	xx (xx.x%)
System Organ Class 3		xx (xx.x%)
	Preferred Term 1	xx (xx.x%)
	Preferred Term 2	xx (xx.x%)
	Preferred Term 3	xx (xx.x%)
System Organ Class 4		xx (xx.x%)
	Preferred Term 1	xx (xx.x%)
	Preferred Term 2	xx (xx.x%)

Table 4  
Medical History  
Full Analysis Set

Characteristic	Overall (N = ##)
ASA Score	
I	xx (xx.x%)
II	xx (xx.x%)
III	xx (xx.x%)
Surgery Indication	

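### The SAP omits two analyses the protocol prespecifies, the maximum-severity AE summary and the prior radiation/chemotherapy subgroup, without saying so

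*Protocol*

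**What the plan says.** **Protocol, AE severity.** The commitment appears twice. Section 5.8, Analysis of Safety, states "All AEs will also be summarized by maximum severity by MedDRA system organ class and preferred term", and the synopsis states "AEs will also be summarized by maximum severity by MedDRA system organ class and preferred term". Section 7.1 defines mild, moderate and severe. Section 7.3 lists "Severity of the event" among the items to record for each AE.

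**Protocol, subgroups.** Section 5.8, Analysis of Subgroups, opens with "Subgroup analyses are planned to be performed for prior radiation therapy/chemotherapy (presence or absence" and goes on to procedure approach and indication for surgery. For each subgroup it promises summary statistics of the procedure-related parameters. Section 3.16 lists radiation/chemotherapy status among the screening data.

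**SAP, AEs.** Section 8.5 says "The number and percentage of subjects reporting AEs and SAEs will be summarized at the MedDRA system organ class and preferred term level". It then adds splits by relationship to device or procedure and by start day. It does not mention severity. It ends with "All reported adverse events will be listed".

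**SAP, subgroups.** Section 8.8 names only surgical approach and surgery indication, for the primary endpoint. Table 28 adds subjects with any potential leak risk factor from the Medical History eCRF.

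**SAP, completeness.** The appendix opens with "Table shells are provided below for all summaries to be generated for this study".

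**The concern.** Protocol 5.1 gives the SAP the task of supplementing the protocol's analyses. Leaving out a named analysis does not supplement it, so a reader would expect either the analysis or a statement that it was dropped and why.

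Safety surveillance is a stated secondary objective, and maximum severity is one of the few ways the protocol planned to describe AEs. Prior radiation or chemotherapy is the first subgroup the protocol names. If the SAP is followed exactly, the report will contain neither result, and nothing in the SAP requires anyone to say so. In a descriptive study with no hypothesis test, the planned summaries are the output, so losing one loses a result.

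**Working it through.** No figure in the plan is in dispute. The check sets the protocol's commitments against the SAP text and its table list.

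**1. AE tables.** Tables 11 to 16 are 6 and Tables 29 to 33 are 5, so 6 + 5 = 11. By title they are:
- all AEs: 11, 29, 31
- all SAEs: 12, 33
- device-related AEs: 13, 30, 32
- device-related SAEs: 14
- procedure-related AEs: 15
- procedure-related SAEs: 16

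That is 3 + 2 + 3 + 1 + 1 + 1 = 11. They divide events by seriousness, relationship and start day. None divides by severity: 0 of 11.

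**2. Severity elsewhere.** Table 10 tabulates Grades A, B and C for post-operative anastomotic leak. That covers one event type on its own grading scale, not all AEs on the scale in protocol 7.1.

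**3. Subgroup tables.** Tables 19 to 22 are surgical approach (4), 23 to 27 are indication (5) and 28 is the pooled risk-factor group (1): 4 + 5 + 1 = 10. None is radiation/chemotherapy present or absent: 0 of 10. Table 28 does not list its factors, has no table for subjects without them, and is not mentioned in SAP 8.8. A presence/absence result cannot be read from it.

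**4. Is either omission stated?**
- The revision history for version 2.0 gives its reason as "Addition of Adverse Event tables to support the submission to NMPA for registration in China". It reopened the AE section for five tables and did not mention severity.
- SAP 2 explains the move to a single arm under amendment 3, which is a different matter.
- SAP 8.1 requires disclosure of analyses that differ from the SAP itself. A report that follows the SAP would trigger nothing.

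**5. Per Protocol Set, side by side.** Protocol 5.6 requires a completed anastomosis and no major deviation. SAP 6 requires Full Analysis Set membership (anastomosis attempted) and no major deviation. The number of non-completed anastomoses, k, is not given, so the size can only be illustrated. Assume 165 subjects, x with an issue and no major deviations. Removing k subjects gives (x − k)/(165 − k) if all k had an issue, and x/(165 − k) if none did. With x = 33:
- k = 0: 33/165 = 20.0% (exact 95% CI 14.2% to 26.9%)
- k = 3: 30/162 = 18.5% to 33/162 = 20.4%
- k = 5: 28/160 = 17.5% to 33/160 = 20.6%

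These shifts are small against the interval.

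**The case against.** The best case for the SAP is as follows.

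- **Severity is not wholly absent.** Leak, the AE with its own documentation section in the protocol, is graded in Table 10, and the SAE tables separate serious events. The first part stands: it would be wrong to infer that no AE severity is tabulated. But seriousness is not severity, and Table 10 does not replace the summary of all AEs.
- **The data are listed.** Listing 18 covers AEs and all collected fields are to be listed. This stands, so nothing recorded is hidden, but a per-subject listing is not the planned summary.
- **Table 28 may include irradiated or chemotherapy-treated subjects.** Possibly. The factors are unlisted, so the overlap is unknown, and there is still no absence group.
- **The protocol's subgroup promise concerns procedure-related parameters, not expressly the primary endpoint.** This stands and shapes the fix: Table 7 shells alone would not deliver what the protocol describes.
- **Data availability is inferred.** The eCRF is not in the documents. SAP Table 4 shows no radiation/chemotherapy item. The relationship categories in SAP 8.5 differ from those in protocol 7.1, so recorded fields need not match the protocol text. This stands as a stated assumption.

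A reader might also infer that the two Per Protocol rules undermine a result. The documents do not support that. The Table 6 row for a non-completed anastomosis may only mirror eCRF options, since the same table has a row for anastomosis not attempted, which must be empty in the Full Analysis Set. Completion may also depend on the device failure being measured, which favours the SAP's rule.

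**Conclusion.** The point holds for two analyses. The SAP leaves out the summary of all AEs by maximum severity and the prior radiation/chemotherapy subgroup, and states neither omission. Its size is two missing descriptive outputs: 0 of 11 AE tables by severity and 0 of 10 subgroup tables by radiation/chemotherapy, with leak grade in Table 10 the only severity-type summary.

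A reader might take this further and infer that the primary result is compromised or that the omissions were deliberate. The documents support neither. No hypothesis is tested, the Full Analysis Set estimate and its Clopper-Pearson interval do not depend on these tables, and the SAP gives no reason for the omissions. The Per Protocol difference merits a one-line clarification and no more.

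The omissions themselves rest on text alone. Only the claim that they can be repaired without new data is an assumption, namely that the eCRF captured AE severity and radiation/chemotherapy status as protocol 7.3 and 3.16 describe.

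**What to change.** In the SAP, carried through to the study report:

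1. Add one table of all AEs by maximum severity, by system organ class and preferred term.
2. Add prior radiation/chemotherapy, present and absent, to SAP 8.8. Provide two tables in the Table 7 layout for the primary endpoint, as the SAP does for its other subgroups, plus the procedure-related parameters promised in the protocol's Analysis of Subgroups.
3. If any part is not provided, say so and give the reason.
4. As a clarification only, add one line to SAP 6 stating that its Per Protocol rule (attempted, no major deviation) replaces the protocol's completion condition.

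The cost is at least 1 + 2 = 3 extra tables, with more if the procedure-related parameters are tabulated separately, and a few lines of text. No new data are needed under the eCRF assumption above.

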### **Handling of Dropouts or Missing Data**

All analyses will be performed only on subjects undergoing the surgical procedure (colorectal anastomosis attempted with a powered circular stapler) and only observed data will be analyzed. There will be no imputation of missing data for any parameters or for early terminated subjects.

### **Data Monitoring Committee**

No data monitoring committee is planned for this study.

### **Multicenter Studies**

No adjustment for center is planned in the statistical analysis. However, center specific analyses may be conducted pending within-center sample size to understand the effect that surgeon techniques and site standard of care may have on the overall results.

### **Analysis of Subgroups**

Subgroup analyses are planned to be performed for prior radiation therapy/chemotherapy (presence or absence), procedure approach (open vs. laparoscopic), and indication for surgery (diverticulitis, neoplasm, etc.). Summary statistics for the procedure-related parameters will be provided for each subgroup. Further subgroups may be defined pending the distributions of baseline demographic and clinical characteristics.

## **6.0 RISKS AND BENEFITS OF THE STUDY**

All procedures will be performed per site standard-of-care. This study may or may not provide any benefits to the subject. No risks will be introduced to subjects outside of those that are already inherent in these types of procedures.

## 7.0 ADVERSE EVENTS

### 7.1 DEFINITIONS

#### Adverse Event

Adverse events will be collected from the time an attempt is made to use the powered circular stapler device. For this study, an AE is defined as any undesirable clinical occurrence in a subject that may be attributable to the study procedure or device used to create the colorectal anastomosis. Only AEs attributable to the device used to create the anastomosis or to the study procedure are to be recorded in the eCRF and reported to the Sponsor.

#### Expected Morbidity/Anticipated Adverse Events

An expected morbidity/procedural complication is defined as an AE that is known to be common or usual in nature, severity, or incidence during left-sided colon surgery. A list of expected AEs (anticipated) that may occur during this study are listed in Appendix II.

#### Serious Adverse Event

It is the Investigator's responsibility to determine the "seriousness" of an AE using the protocol defined terms below. A serious adverse event/injury is an AE that results in one or more of the following for this study:

- Life-Threatening: The subject was at imminent risk of dying at the time of the adverse event.
- Permanent Impairment: An adverse event that resulted in permanent impairment of a body function or permanent damage to a body structure.
- Necessitated Intervention: An adverse event that resulted in a condition that necessitated medical or surgical intervention to preclude permanent impairment of a body function or damage to a body structure.
- Required in-patient or prolonged hospitalization.
- A persistent or significant disability or incapacity.
- Resulted in Death: An adverse event that resulted in the subject's death.

Note: "Death" should not be reported as an adverse event. The cause of death should be reported as an adverse event. The only exception is "Sudden Death" when the cause is unknown. NOTE Planned hospitalization for a pre-existing condition, or a procedure required by the protocol, without serious deterioration in health, is not considered a serious adverse event.

#### Severity of Adverse Events

It is the Investigator's responsibility to assess the severity of an AE. A change in severity may constitute a new reportable AE.

The following guideline should be used to determine the severity of each adverse event:

- **MILD:** Awareness of signs or symptoms, but does not interfere with the subject's usual activity, or is transient which resolves without treatment and with no sequelae.
- **MODERATE:** A sign or symptom, which interferes with the subject's usual activity.
- **SEVERE:** Incapacity with inability to do work or usual activities.

### **Relationship of Adverse Events**

It is the Investigator's responsibility to assess the relationship between all AEs and the study procedure or circular staplers used in the study. Only AEs attributable (relationship of possibly, related, or unknown) to a device or the study procedure are to be recorded in the eCRF and reported to the Sponsor.

The following guidelines should be used in determining the relationship of an adverse event to a device, study procedure, or other causality:

- **Possibly** – A clinical event (including abnormal laboratory result) that presents an unlikely association between device/procedure, which cannot be ruled out with certainty, but could also be explained by alternative etiology;
- **Related** – A clinical event (including abnormal laboratory result) that presents a strong temporal relationship between device/procedure, in which an alternative etiology is unlikely; or
- **Unknown** – A clinical event (including abnormal laboratory result) that cannot be determined to be related or unrelated to device/procedure given the information obtained.

## **7.2 REPORTING PROCEDURES FOR ADVERSE EVENTS**

### **7.3 RECORDING ADVERSE EVENTS**

The Investigator will record all device- or procedure-related AEs considered attributable (relationship of possibly, related, or unknown) to the powered circular stapler or to the procedure in the source documents and associated eCRF. The site must complete the AE CRF within two weeks of becoming aware of an event and SAE eCRF within 72 hours of becoming aware of the event. Supporting SAE documentation should be de-identified and emailed to the Clinical Study Lead.

Standard medical terminology should be used when recording AEs. In addition, the following information should be recorded:

- Onset Date
- Resolution date or date of death
- Severity of the event
- Action Taken
- Event Status (ongoing at study end or resolved)
- Relationship of AE to a surgical device used in the study
- Relationship of AE to the study procedure
- Indication of whether the event is serious

Data related to SAEs will be collected until event resolution, or until the event is considered stable, or until all attempts to determine the resolution of the event are exhausted. All AEs that are unresolved at study completion (or early termination) will be recorded as ongoing at study end.

The Investigator will be required to assess if the SAE is considered anticipated (Appendix II) and if the event involved a product complaint. The report of an SAE by a site does not constitute an admission that study personnel or the user facility (hospital/clinic) caused or contributed to the event. The study site is also responsible for submitting to the reviewing IRB/EC according to their IRB/EC procedures.

The Investigator will be required to assess if the SAE is considered anticipated (Appendix II) and if the event involved a product complaint. The report of an SAE by a site does not constitute an admission that study personnel or the user facility (hospital/clinic) caused or contributed to the event. The study site is also responsible for submitting to the reviewing IRB/EC according to their IRB/EC procedures.

